## 5.4 STRATEGIES FOR RECRUITMENT AND RETENTION

Recruitment will occur through the NYU Langone Child Study Center and Comprehensive Epilepsy Center. Both sites have a good track record for recruitment of participants with ASD, and will use all successful recruitment methods as previously demonstrated, including use of a study flyer that will be available in the lobbies of the Child Study Center and the Comprehensive Epilepsy Center as well as published online. We expect to accrue the sample of 30 within 22 months of study initiation. If accrual slows at any time point during the study, additional staff effort and resources will be dedicated to recruitment efforts including attendance at autism support groups and events and the use of tools such as google search engine optimization. We will also employ an EHR query through NYU Langone Health's DataCore for individuals with an ASD diagnosis and will contact these individuals using the IRB-approved direct mail text (see 18-00250 direct mail recruitment notification). Only the pIs, co-I's, and other research personnel listed on the study will have access to information regarding potential participants.

Interested parents/legal guardians will speak with study staff over the phone for the purpose of screening to determine basic inclusionary and exclusionary information prior to scheduling a screening visit. If the parent/legal guardian endorses any exclusionary criteria or fails to endorse

inclusionary criteria over the phone, then the study staff will inform them that the study would not be appropriate. If the parent/legal guardian does not endorse any exclusionary criteria and endorses all inclusionary criteria, then the study staff will schedule the screening visit. Of note, if the child does not qualify for the study as a result of pre-screening or the family decides not to proceed with the study after pre-screening, their data will be discarded and will not be used in this research. We aim to obtain complete datasets from at least 30 child and adolescent participants with HFA. To reach this number, we anticipate enrolling up to 50 children for in-person screening visits to assess variables related to inclusionary and exclusionary criteria. Approximately five children will be screened for eligibility to enter each cohort of size 3. Therefore, screening visits will be scheduled across time, as each prior cohort approaches participation completion.

We will recruit and include both males and females. The male to female prevalence ratio for ASD without intellectual disability is estimated at approximately 5:1 (10); therefore, we will aim to recruit at least 15% female participants (n=4 to enroll; n=8 to screen) by prioritizing prospective female participants. In regard to age, this study is intended to examine the CBD dose response in a child and adolescent population. Therefore, youth aged 7 years to before their 18th birthday at the time of projected end of the trial will be recruited to participate. We aim to recruit participants across this age range to ensure representation of developmental stages. Finally, individuals of all races and ethnic origins are eligible for participation in this study. Based upon the demographics of prior ASD study samples at the NYU Child Study Center, we expect approximately 15% of participants to self-identify as Hispanic/Latino, and racial composition of participants to be approximately 64% Caucasian, 20% African American or Black, 4% Asian, 1% Native Hawaiian or Other Pacific Islander, <1% American Indian, and 10% more than one race.

This trial focuses on children and adolescents with HFA because of the greater potential for benefit in ASD core and associated symptoms in children and adolescents than in adults, balanced with the relatively low AE profile of CBD. The lower age limit is defined by feasibility of obtaining cooperation for extensive study procedures. In compliance with IRB standards for research with vulnerable populations, a description of risks and benefits is included in the protocol. We will not enroll emancipated minors or mature minors and will therefore require written consent by a parent or legal guardian as well as child assent, in accordance with IRB regulation.

Parents/guardians of participants will be compensated for study participation, subject to IRB approval, at the rate of \$75/visit for the enrollment/baseline, week-4 and final visits, and \$40/visit for the other two visits. If they agree to participate in optional MRI scanning, they will also be compensated \$75 for each scan. A \$10 stipend will also be provided for visits that include blood draws and MRI scans (e.g., Screening Visit, Baseline Visit, Week-4 Visit if indicated, Week-6 Visit) to cover any additional travel expenses. This practice is standard for research projects which require substantial effort, and serves to distinguish research from standard clinical practice.

In addition to compensation and because the study will occur across approximately 10 weeks, participants will receive visit reminders to enhance participant retention. Further, multiple methods including telephone calls and secure email will be used for contacting participants throughout the study.

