## 4 STUDY DESIGN

### 4.1 OVERALL DESIGN

The primary objective is to determine the optimal dose of CBD in children and adolescents with ASD; the hypothesis is that doseresponse curve may not be linear and that moderate doses of CBD may be therapeutically beneficial for core and associated symptoms in children and adolescents with ASD. The second objective of this study is to determine effect sizes for a variety of outcome measures, with the longer term goal of facilitating the selection of primary and secondary outcome measures for a subsequent placebo-controlled RCT. The third objective is to assess the feasibility of quantifying candidate biomarkers (e.g., resting-state functional connectivity) using MRI.

This single group single-site study will seek to enroll youth between the ages of 7 and 17 years who have a diagnosis of ASD with broadly average intelligence and who are fluently verbal. An adaptive design will be employed to allow for evaluation of optimal dosing while collecting data on core and associated ASD symptoms and any Aes that may present. Under the adaptive design algorithm we implemented, we ended recruitment after enrolling 15 participants and testing two doses. Given the higher rate of response on the higher of the two doses tested (44% vs. 16%), and the suggestion that higher doses of CBD may particularly target dopamine type 2 high affinity receptors (D2Rhigh) in the striatum, we have modified the study by implementing part 2 (described further on page 17-20), to recruit up to 15 youth (within the previously approved total accrual of 30 who would enroll) with clinical profiles that most closely resemble youth classified as responders in Part 1 of the trial.

It is important to note that all endpoints in this study are exploratory; the research base is too limited to make confident predictions. Nonetheless, given the lack of alternative pharmacological options, the benign AE profile, and the potential for CBD to fill this treatment gap, this line of work is necessary to direct future research in the field.

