#### 4.3 JUSTIFICATION FOR DOSE

Chronic CBD dosing up to 1500 mg/day has been reported to be tolerated well without AE (60-63); minor AE were reported after CBD use in children with epilepsy being treated with multiple other medications in doses up to 50 mg/kg/day (3, 27). Accordingly, we believe an upper limit of 9 mg/kg/day orally in our dose finding approach is reasonable and safe. Our proposed dosage range is substantially lower than most pediatric studies registered in ClinicalTrials.gov (accessed on 06 February 2018). Our dose range (3-9 mg/kg/day) is comparable to the only ongoing study specifically addressing behavioral symptoms in ASD (NCT02956226; dose range 1 mg/kg/day to 10 mg/kg/day). As mentioned, participants assigned to the highest dose (9 mg/kg/day) will be instructed to take half the dose (4.5 mg/kg/day, divided in two doses) per day for the first week of treatment before increasing to the full dose to minimize the chance for adverse events upon treatment initiation. This will go into effect when the next cohort of participants begin treatment with CBD; therefore, all participants who have already been enrolled will not be re-consented or informed of the changes.

The BOIN design, discussed in detail within the Dosing and Administration section of the protocol, was informed by the observation of dose-dependent inverted-U effects on social behavior in a mouse model of Dravet syndrome in which social effects were observed at lower doses than anti-seizure effects (2), the increased efficacy of CBD in reducing anxiety during a public speaking task at a moderate dose compared to a low and high dose (9), and correspondence with [name] regarding his clinical experiences in prescribing CBD to address associated symptoms of ASD. As noted, now that we've obtained data from 15 participants on the low and intermediate doses by implementing the BOIN design, we propose to test the remaining 9 mg/kg/day dose in up to 15 participants – within the originally approved accrual ceiling of 30.

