## 7.2 PARTICIPANT DISCONTINUATION/WITHDRAWAL FROM THE STUDY

A participant may be discontinued from study treatment at any time if the participant or participant's legal guardian or the investigator feels that it is not in the subject's best interest to continue. The following is a list of possible reasons for study treatment discontinuation:

- Parental/guardian withdrawal of consent
- Subject is not compliant with study procedures
- Protocol violation requiring discontinuation of study treatment
- SAE, including significant toxicity such as severe cognitive or behavioral toxicity, impaired liver function, or impaired hematopoiesis that is deemed to be potentially or likely related to study medication

If subject must come off of study treatment, the method of CBD discontinuation will be determined based on type of reaction and/or reason for withdrawal. For example, if the participant experiences a rapidly progressive rash it would lead to abrupt cessation of CBD, but if participant experiences excess tiredness, CBD would be tapered off. A discussion of the method of cessation will occur between the participant and/or participant's parent/legal guardian and the physician.

Subjects for whom a parent/guardian has signed the informed consent form, who have received the study intervention, and subsequently withdraw, or are withdrawn or discontinued from the study will not be replaced.

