### 9.2 SAMPLE SIZE DETERMINATION

No statistical methods were used to determine the sample size for this study. The total number of participants expected to participate at NYU Child Study Center and Comprehensive Epilepsy Center is 30.

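### Thirty is stated as the sample, the expected number and a floor for complete datasets, but it is the accrual ceiling and the design does not ensure it

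*Combined protocol and SAP*

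**What the plan says.** Four places give 30 as the size the trial will have. The synopsis (1.1, Study Population) says the sample will include 30. The schema (1.2) gives 30 as the total enrolled, in 10 cohorts. Section 5.4 sets a floor: "We aim to obtain complete datasets from at least 30 child and adolescent participants with HFA". Section 9.2 says "The total number of participants expected to participate at NYU Child Study Center and Comprehensive Epilepsy Center is 30", and also "No statistical methods were used to determine the sample size for this study".

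Other sections make 30 an upper limit. Section 4.1 reports that in Part 1 "we ended recruitment after enrolling 15 participants and testing two doses" and plans no more than 15 further participants, "within the previously approved total accrual of 30 who would enroll". Section 4.3 describes the Part 2 participants as falling "within the originally approved accrual ceiling of 30". Section 7.2 provides that participants who have received study drug and then withdraw "or are withdrawn or discontinued from the study will not be replaced".

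Section 6.1.2 commits Part 2 to at least six participants. With Table 3, it ends the trial if cumulative responders, counting the five from Part 1, number no more than 5 at 21 participants, 6 at 24 or 7 at 27.

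**The concern.** A quantity capped at 30 cannot also have 30 as its floor, except by being exactly 30. That requires no futility stop and, if a complete dataset means a child followed through to the end, no lost participant. Nor is a maximum an expectation when the plan's own Table 4 gives a non-zero chance of stopping early at every rate shown.

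What is at stake is the stated size and the precision a reader infers from it. The 9 mg/kg/day response rate will rest on 6 to 15 participants, and the pooled secondary effect sizes on 21 to 30. Section 9.2, where a reader looks for the sample size, does not say that the trial may end at 21.

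**Working it through.** **Inputs**
- Part 1: 15 enrolled, 5 responders (4.1, 6.1.2).
- Part 2: cohorts of 3, at most 15 participants (4.1, 4.3, Table 3).
- Stopping rule after subtracting the 5 Part 1 responders: 0 of 6, at most 1 of 9, at most 2 of 12 (6.1.2, Table 3).
- True response rates p: 0.1 to 0.5 (Table 4), and 1/3, the minimum anticipated in 6.1.2.
- Dropout rate: not given.

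**Formulas**, with q = 1 − p:
- Stop at 21: S6 = q^6.
- Stop at 24: one responder in the first six, none in the next three. S9 = 6·p·q^8.
- Stop at 27: two responders in the first nine, none in the next three. Of the 36 placements of two responders among nine, 3 put both in the third cohort, and those paths have already stopped at six. That leaves 33, so S12 = 33·p²·q^10.
- P(30 enrolled) = 1 − (S6 + S9 + S12).
- Expected total = 15 + 6·S6 + 9·S9 + 12·S12 + 15·P(30).

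**At p = 1/3:** S6 = 0.0878, S9 = 0.0780 and S12 = 0.0636, which sum to 0.2294. P(30) = 0.7706. Expected total = 15 + 0.527 + 0.702 + 0.763 + 11.559 = 28.55, or 28.6.

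**All rates, before any dropout:**

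| True rate | Early termination, Table 4 (%) | Early termination, exact (%) | Stop at 21 / 24 / 27 (%) | P(30 enrolled) (%) | Expected total |
|---|---|---|---|---|---|
| 0.1 | 90.4 | 90.5 | 53.1 / 25.8 / 11.5 | 9.5 | 23.3 |
| 0.2 | 60.8 | 60.5 | 26.2 / 20.1 / 14.2 | 39.5 | 26.0 |
| 0.3 | 31.0 | 30.5 | 11.8 / 10.4 / 8.4 | 69.5 | 28.1 |
| 1/3 | not given | 22.9 | 8.8 / 7.8 / 6.4 | 77.1 | 28.6 |
| 0.4 | 11.9 | 11.9 | 4.7 / 4.0 / 3.2 | 88.1 | 29.2 |
| 0.5 | 3.5 | 3.5 | 1.6 / 1.2 / 0.8 | 96.5 | 29.8 |

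The exact early-termination probabilities agree with Table 4 to within 0.5 percentage points, so the rule has been read as the plan intends.

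**Dropout (assumed).** The 50 screening places in 5.4 cover screen failures only: at about five screened per three enrolled, 50 × 3/5 = 30. Take the 15 Part 1 participants as complete, since 4.2 reports that all completed treatment. Let each Part 2 participant be lost independently with probability d. Then P(30 complete) = P(30 enrolled) × (1 − d)^15. At a response rate of 1/3:
- d = 2%: 0.7706 × 0.7386 = 57%.
- d = 5%: 0.7706 × 0.4633 = 36%.
- d = 10%: 0.7706 × 0.2059 = 16%.

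**The case against.** The plan already discloses most of this. Sections 4.1 and 4.3 present 15 as an upper limit for Part 2 and 30 as the overall limit. Section 6.1.2 sets out each stop and tabulates its probability, and 9.4.2 refers the reader to Tables 3 and 4. Section 5.4 states an aim in a recruitment section, and the expected number in 9.2 can be read as a planning count rather than a mathematical expectation. All of that is fair, and nothing in Table 4 is miscalculated. But these disclosures show the inconsistency rather than remove it, because the four statements of 30 were not brought into line with them.

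The dropout figures are weaker evidence. The plan does not define a complete dataset. Section 7.1 schedules the symptom measures at discontinuation, and 9.4.3 uses the last observation after early termination, so a child who stops treatment need not be lost to analysis. Section 7.1 also counts adverse-event discontinuations as non-responders. Dropout and futility stopping are therefore not independent, as the calculation assumes. The figures are illustrations only.

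A reader might also infer that the secondary effect sizes rest on Part 2 alone. The documents do not support that: 9.3 analyses all participants and 9.4.3 makes no restriction to Part 2. Only the SWAN is confined to Part 2.

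**Conclusion.** The inconsistency stands, and it is minor. Thirty is a maximum that is presented as a floor and as an expectation. The expected total is below 30 at every rate in Table 4, from 23.3 at 0.1 to 29.8 at 0.5, and is 28.6 at 1/3. These enrolment figures need only the stated stopping rule and a constant, independent response probability across Part 2 participants. The figures for complete datasets rest in addition on the assumed dropout rates.

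A reader might go further and conclude that the trial cannot reach 30, or that a promised 15 in Part 2 has been broken. Neither follows. Thirty is attainable and, at the anticipated 1/3, is the likeliest enrolled total at 77.1%. The plan never guarantees 15 in Part 2. Nor is any power claim affected, since the sample size was not derived statistically.

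**What to change.** In the synopsis (1.1), the schema (1.2), 5.4 and 9.2, state:
- a maximum of 30 enrolled;
- possible totals of 21, 24, 27 or 30 under the Part 2 rule;
- an expected total of about 23 to 30 across all of Table 4's rates, and 28.6 at 1/3, before dropout.

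In 5.4, replace the floor of 30 complete datasets with complete datasets from up to 30. It would help to add in 9.2 that the 9 mg/kg/day response rate will rest on 6 to 15 participants and the pooled secondary effect sizes on 21 to 30.

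This is a change of wording only; the design, the stopping rule and the analyses stay as they are. The cost is a slightly less favourable stated size.

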## 6 STUDY INTERVENTION

## 6.1 STUDY INTERVENTION(S) ADMINISTRATION

### 6.1.1 STUDY INTERVENTION DESCRIPTION

Pure CBD is extracted from the plant *Cannabis sativa*. The most common elements for potential therapeutic use extracted from this plant include  $\Delta^9$ -THC and CBD. Tetrahydrocannabinol (THC) is the main psychoactive element found in *Cannabis sativa*, while CBD has **no psychoactive properties**. Pure CBD can be found as a white crystalline solid. Figure 1 shows its chemical structure.

[figure not shown]

Figure 1. Cannabidiol Structure

The CBD will be Greenwich Biosciences, Inc.'s formulation of 100 mg/mL purified oral solution, dissolved in the excipients sesame oil and anhydrous ethanol with added sweetener (sucralose) and strawberry flavoring. The drug is formulated from extracts prepared from *Cannabis sativa* L. plants that have a defined chemical profile and contain consistent levels of CBD as the principal phytocannabinoid. Extracts from these plants are processed to yield pure (>95%) CBD that typically contains less than 0.5% (w/w) THC.

Cannabidiol is excreted in the urine and feces. The plasma peaks vary significantly between individuals but are typically between 1 to 3 hours (52). The half-life has been reported to be 2-5 days (64).

### 6.1.2 DOSING AND ADMINISTRATION

In regard to drug administration, participants will be required to take Epidiolex with food. Of note, symptoms of food selectivity and food refusal are seen frequently in ASD (65). Therefore, if caregivers report that their child has initial difficulties accepting the CBD, the study clinicians will work on increasing participant tolerance and acceptance of the CBD through the use of standard behavioral intervention strategies for up to one week. If the participant continues to reject the dose he/she was assigned after one week of trial initiation, he/she will be withdrawn from the study.

Related to dosing, in Part 1 of the study, we employed the BOIN design (66, 67) in the first five cohorts of this open trial to estimate the optimal dose. The BOIN design was selected because it is more flexible than the traditional 3+3 design and possesses superior operating characteristics that are comparable to those of the more complex model-based designs, such as the continual reassessment method (CRM) (68).

We defined a target response rate for the optimal dose is  $\phi = 0.60$  and a maximum sample size of 30. We enrolled and treated participants in cohorts of size 3. The trial design was implemented through the following three steps:

1. Participants in the first cohort were treated at Dose Level 2 (see Table 1).
2. To assign a dose to the next cohort of participants, we conducted dose escalation/de-escalation according to the rule displayed in Table 2, which minimizes the probability of incorrect dose assignment with response rates of  $\phi_1 = 0.684$  and  $\phi_2 = 0.52$  designated as the uncertainty interval. When using Table 2, please note the following:
  - a. "Eliminate" means that we eliminate the current dose from the trial to prevent treating any future participants at this dose because the response rate is too low.
  - b. When we eliminate a dose, automatically de-escalate the dose to the next lower level.
  - c. If none of the actions (i.e., escalation, de-escalation or elimination) is triggered, we treat the new participants at the current dose.
  - d. If the current dose is the lowest dose and the rule indicates dose de-escalation, treat the new participants at the lowest dose.
  - e. If the current dose is the highest dose and the rule indicates dose escalation, treat the new participants at the highest dose.
3. Repeat step 2 until the maximum sample size of 30 is reached.

**Table 1.** Dose levels

Dose Level 1	Dose Level 2	Dose Level 3
3 mg/kg/day	6 mg/kg/day	9 mg/kg/day

**Table 2.** Dose escalation/de-escalation/elimination rules for the BOIN Design and results in the first 5 cohorts

Cohort	1	2	3	4	5	6	7	8	9	10
Number of participants treated at the current dose	3	6	9	12	15	18	21	24	27	30
Dose administered (mg/kg/d)	6	6	3	3	6	-	-	-	-	-
Cumulative N of respondents	1	3	4	4	5	-	-	-	-	-
Escalate if # of responses >=	3	5	7	9	11	13	15	17	19	21
Deescalate if # of responses <=	NA	3	4	6	7	9	10	12	14	15
Eliminate if # of responses <=	NA	1	2	4	5	7	8	10	12	13

For purposes of the study design, participants were categorized as either “responders” or “non-responders” at the end of the 6-week intervention phase in order to determine the dose level for the following cohort. This categorization was based upon the following procedures.

- After completing and meeting eligibility criteria, study staff (including child psychologists and psychiatrists with expertise in ASD and comorbid symptoms) met to consensus on an individualized, primary outcome variable for each participant at the enrollment/baseline visit. The primary target was what is most interfering in the child’s functioning at the time of assessment and chosen based upon informant report, scores from a battery of standardized assessments covering a wide range of core and associated symptom

- domains, and clinical observations. Clinician consensus also yielded a Clinical Global Impression-Severity (CGI-S) score to represent the study team's impression of the participant's current severity of illness.
- After the final study visit, study staff met again to consensus on the degree of improvement observed in the predetermined primary outcome variable for each child. A CGI-S score was also determined. Definitions of response and non-response are provided below.
    - Response: In the absence of dose limiting effects, a Clinical Global Impression Scale – Improvement (CGI-I) score of 1 (very much improved) or 2 (much improved) determined by consensus based upon clinical judgment, informant report, and change in scores on measures (using the Reliable Change Index when possible) relevant to the predetermined primary outcome.
    - Non-response: no-to-minimal therapeutic benefit captured by a CGI-I score of 3 (minimally improved) or greater (i.e., no change or any worsening) determined by consensus as indicated above, and/or severe AE, defined as severe cognitive or behavioral toxicity, impaired liver and renal function, or impaired hematopoiesis that is deemed to be potentially or likely related to study medication (also see section 8.3.2), causing early discontinuation of study intervention.

While applying a uniform statistically derived algorithm for defining treatment response and non-response for all patients would have been preferable, the above procedures were implemented given the exploratory nature of the study and the wide range of therapeutic effects that CBD may exert. The intent of this exploratory study has been to provide the foundation for a well-defined subsequent RCT.

Over the first 15 participants, we have identified five as responders, for an overall response rate of 33%, and a response rate of  $4/9 = 44\%$  on 6 mg/kg/day, as opposed to the 60% rate anticipated on the optimal dose. The response rate on 3 mg/kg/day was  $1/6 = 16\%$ . Per the BOIN design that we implemented, we have excluded both the 6 mg/kg/day and 3 mg/kg/day dose for further testing. We believe that it would be scientifically valuable to test the 9 mg/kg/day dose on the remaining 15 participants that were originally approved for this open trial. The purpose would be to further confirm the overall safety of the AE profile – which is likely given the pediatric experience with 10 mg/kg/day and 20 mg/kg/day in patients with refractory epilepsy who are more medically fragile. It has also been hypothesized that higher doses of CBD may have preferential effects on D2high receptors in the striatum. If so, that might explain why all five responders had ASD, as well as ADHD.

Accordingly, we now request that we amend the open trial to test only the dose of 9 mg/kg/day and that we require the combination of ASD and ADHD for inclusion. All other aspects of the trial would be unchanged, other than adding the Strengths and Weaknesses of Attention-Deficit/Hyperactivity Disorder Symptoms and Normal Behavior (SWAN) as a dimensional measure of ADHD and completing the K-SADS-COMP at the screening visit rather than the baseline/enrollment visit so that the study clinicians can confirm the presence of an ADHD diagnosis.

Given our experience with the first 15 participants, we anticipate that at least 1/3 will be classified as responders. If none of the first 6 participants on 9 mg/kg/day are responders, then we would eliminate the dose and terminate the trial. A low, non-zero response rate, as shown below in Table 3, would also determine terminating the trial, as it would be tantamount to evidence that the optimal dose was 6 mg/kg/day, our initial starting dose.

**Table 3.** Dose elimination rules for cohorts 6 to 10

Cohort	1	2	3	4	5	6	7	8	9	10
Number of participants to be treated at the current dose	3	6	9	12	15	18	21	24	27	30
Dose administered (mg/kg/d)	6	6	3	3	6	9	9	9	9	9
Cumulative N of respondents	1	3	4	4	5	-	-	-	-	-
Terminate if # of responses <=						NA	5	6	7	

Thus, we propose to enroll at least six more participants on the dose of 9 mg/kg/day. If none of them respond, the cumulative number of respondents would remain 5, and we will discontinue the trial; if at least 1 responds within the first 6, we will enroll 3 additional participants. If the total number of responders remains 6, we will discontinue the trial. If the number of responders is 7 or more after 9 participants are enrolled, we will enroll an additional 3 participants for a total of 12 on this dose. If the number of responders does not increase beyond a total of 7, we will terminate due to likely futility.

Table 4 provides the operating characteristics of this design extension for a variety of true response rates.

**Table 4.** Operating characteristics of 9 mg/kg/day evaluation

	Dose 1	Dose 2	Dose 3	Dose 4	Dose 5
True response rate	0.1	0.2	0.3	0.4	0.5
Probability of early termination(%)	90.4	60.8	31.0	11.9	3.5

